#### 1. AMENDMENTS FROM PREVIOUS VERSION(S)

Not applicable.

#### 2. INTRODUCTION

This document describes the planned statistical analyses for Protocol B7861002. This analysis plan is meant to supplement the study protocol. In this document, any text taken directly from the protocol is italicized. Any deviations from this analysis plan will be described in the Clinical Study Report (CSR).

#### 2.1. Study Overview

PF-06747143 will initially be developed in patients with acute myeloid leukemia (AML). The diagnosis of AML will be according to the World Health Organization (WHO) classification (Ref (8). The study will be conducted in two parts, Part 1 single agent dose escalation and Part 2 PF-06747143 in combination with standard chemotherapy with an option for single agent cohort expansion at the RP2D.

Assessment of anti-leukemia activity of PF-06747143 will be based on Diagnosis and management of acute myeloid leukemia in adults: recommendations from an international expert panel, on behalf of the European LeukemiaNet. (Ref (2).

#### 2.1.1. Part 1

Part 1, dose escalation, is an open-label, multi-center, single arm, non randomized, multiple dose, safety, pharmacokinetic and pharmacodynamic study of single-agent PF-06747143 in sequential dose levels of adult patients with refractory and/or relapsed AML in order to establish MTD/ RP2D or maximally permitted dose (MPD).

Patients will receive PF-06747143 as a weekly infusion (QW) in 28 day cycles at escalating doses. The proposed dosing scheme includes 0.3, 1.0, 3.0, 10, 15, and 20 mg/kg. Patients enrolled in the first two dose levels (0.3 mg/kg and 1.0 mg/kg) will be required to stay in the clinic/hospital overnight (minimum of 24 hours) after receiving the first dose of PF-06747143 to monitor for the potential risk of hyperleukocytosis that might be caused by the inhibition of by PF-06747143. On an individual basis, patients may be monitored overnight for the additional doses in Cycle 1 at the treating physician's discretion.

[figure not shown]
In the first three dose levels (ie, starting dose 0.3 mg/kg through 3.0 mg/kg), initiation of the first dose of PF-06747143 for each patient in the dose level must be at least 72 hours after the first dose of the previous patient. Patients enrolled in subsequent dose levels will be treated on an outpatient basis with no staggering of patients unless there are safety concerns based on findings at the lower doses.

Once MTD or MPD is identified, additional patients may be enrolled at that dose level (to a minimum of 9) to further investigate the anti-leukemia activity, safety, and PK profile of PF-06747143 prior to an expansion cohort with single agent PF-06747143 at the MTD/MPD/RP2D.

The total estimated number of patients to be enrolled for the Part 1 dose escalation study will be approximately 30-50 patients but it is pertinent to recognize that the exact sample size of the mTPI design in Part 1 cannot be pre specified in advance because it is a dynamic feature of the design.

Once the dose of 15 mg/kg in Part 1 is found safe and tolerable, the Part 2 combination cohorts will be initiated at 10 mg/kg while the Part 1 single agent dose escalation continues to 20 mg/kg for MPD or MTD assessment.

Figure 1. Part I schema

#### 2.1.1.1. Starting Dose

The starting dose will be 0.3 mg/kg, administered QW in 28 day cycles.

#### 2.1.1.2. Criteria for Dose Escalation

A modified toxicity probability interval method (mTPI) (Ref (7)) targeting a DLT rate of 25% with an equivalence interval (20%-30%) will be utilized in order to estimate MTD in dose escalation. For all dose levels, patients may be enrolled in cohorts of 2-4 (the target size of each cohort will be 3 patients). Intermediate dose levels to further evaluate the safety and/or PK may be evaluated following discussion between sponsor and Investigator.

The dose levels planned for Part 1 of the study are shown in Table 1 Additional dose levels may be explored, if appropriate based on emerging safety, PK or PD data. Intra-patient dose escalation of PF-06747143 or the backbone chemotherapy (in Part 2 combination cohorts) will not be permitted.

**Table 1. Possible Dose Levels** 

Dose Level	PF-06747143 Dose (mg/kg) (QW)
1	0.3
2	1.0
3	3.0
4	10
5	15
6	20

The mTPI method relies upon a statistical probability algorithm, calculated using all patients treated in prior and current cohorts at the same dose level to determine where future cohorts should be on dose escalation, no change in dose, or dose de escalation. The algorithm will stop if any of the following criteria is met:

- the maximum sample size has been achieved (approximately 50 patients total);
- at least 9 patients have been accumulated on a dose that is predicted to be the MTD;
   or
- all doses explored appear to be overly toxic and the MTD cannot be determined.

Although dose levels are capped at 20 mg/kg, this mTPI will continue to operate subject to the constraints detailed above while allowing for doses higher than specified. All clinically relevant adverse events (AEs) and serious adverse events (SAEs) will be reviewed by the Sponsor and Investigators after each dose level is complete to determine if the dose allocation schedule requires modification.

The modified toxicity probability interval (mTPI) design uses a Bayesian statistics framework and a beta/binomial hierarchical model to tailor dose-escalation and de-escalation decisions.(Ref 7) These rules are conceptually similar to those used by the 3+3 design and all thedose-escalation decisions for a given trial and can be pre-calculated under the mTPI design and presented in a two-way table (Appendix 4).

Patients will continue with study treatment until disease progression, patient refusal or unacceptable toxicity occurs. Patients experiencing a DLT may be managed with dose modification (after dose interruption) or discontinuation. Subsequent dose levels may not be opened until all patients entered at the current dose level have been treated and observed for at least one complete cycle and the number of DLTs among those patients in their first cycle has been determined. Intra-patient dose escalation will not be permitted in this study.

#### 2.2. Part 2

Part 2 dose expansion, is an open-label, multi-center, non randomized study to assess the safety and tolerability and preliminary anti-leukemia activity of PF-06747143 in three cohorts (two combination cohorts and one potential cohort of single agent PF-06747143).

Figure 2.

Part 2 will assess the safety and tolerability and preliminary anti-leukemia activity of PF-06747143. In Part 2, PF-06747143 will be administered at 10 mg/kg QW (Section 3.1.2.1) on 28 day cycles in combination with chemotherapy in two separate cohorts each containing up to 30 patients with newly diagnosed AML, including Cohort 1 in fit treatment naïve AML patients, in which PF-06747143 will be combined with standard intensive 7+3 chemotherapy with cytarabine (100-200 mg/m2 continuous infusion for 7 days) and daunorubicin (60-90 mg/m2 daily for 3 days), and Cohort 2 in unfit treatment naïve AML patients who are considered to not tolerate or decline to receive standard intensive 7+3 treatment, in which case PF-06747143 will be combined with standard dose of azacitidine (75 mg/m2 administered subcutaneously or intravenously daily for 7 days) or decitabine (20 mg/m2 by continuous intravenous infusion over 1 hour daily for 5 days in a 4-week schedule) based on drug availability and institutional guidance.

Attributions to fit or unfit in Part 2 will be based on "Consensus-based definition of unfitness to intensive and non-intensive chemotherapy in acute myeloid leukemia: a project of Italian SIE, SIES and GITMO group on a new tool for therapy decision making"25 per Investigator judgement.

An additional single agent PF-06747143 expansion cohort, Cohort 3, at the MTD/RP2D may be initiated in Part 2 in 15-30 refractory and/or relapsed AML patients based on single agent PF-06747143 clinical benefit in Part 1.

#### 2.2.1. Part 2 Combination Cohorts Starting Dose

After the DLT observation period in the first cycle of 15 mg/kg cohort is cleared, the dose of 10 mg/kg of PF-06747143 will be used to initiate the Part 2 combination studies, which may be escalated or de-escalated, depending on emerging data. Additionally, if an MTD in Part 1 is determined at or below the dose of 15 mg/kg, a lower dose than 10 mg/kg may beconsidered to move into Part 2 dose expansion combination studies.

#### 2.2.2. Part 2/Cohort 1 and 2

In Part 2, Cohort 1 and 2 expansion cohorts (E) will start with a safety lead-in (S) in approximately 3-6 patients to assure the combination treatment regimen is safe and tolerable in each patient population (ie, fit and unfit AML). The safety lead-in will use the standard 3+3 dose escalation method to evaluate safety profile (using the DLT criteria described in Section 3.1.1.3) for a duration of up to 2 cycles.

# 2.2.2.1. Part 2/Cohort 1 - PF-06747143 Combination in Fit Treatment Naïve AML Patients

Cohort 1 safety lead-in group (S1) will start with 10 mg/kg dose of PF-06747143 and may be escalated to up to 20 mg/kg (the MPD) or de-escalated to below 10 mg/kg based on the predefined DLT criteria (see Section 3.1.1.3) and emerging data. After completion of the S1 cohort, PF-06747143 will be administered in combination with intensive therapy (ie, 7+3 daunorubicin and cytarabine) as induction and continue during consolidation and in maintenance for up to a maximum of 6 months (6 cycles) starting from the completion of consolidation, until disease progression or relapse, patient refusal or unacceptable toxicity occurs (whichever comes first) in newly diagnosed treatment naïve fit AML patients. The expansion cohort (E1) will enroll up to 30 patients.

# 2.2.2.2. Part 2/Cohort 2 – PF-06747143 Combination in Unfit Treatment Naïve AML Patients

Cohort 2 safety lead-in group (S2) will start with 10 mg/kg dose of PF-06747143 and may be escalated to up to 20 mg/kg (the MPD) or de-escalated to below 10 mg/kg based on the predefined DLT criteria (see Section 3.1.1.3) and emerging data. After completion of the S2 cohort, PF-06747143 will be administered in combination with a hypomethylating drug (ie, either azacitidine or decitabine, based on institutional guidelines) and may continue for up to 1 year (~12 cycles) from start of therapy or until disease progression or relapse, patient refusal or unacceptable toxicity occurs (whichever comes first) in newly diagnosed treatment naïve unfit AML patients). The expansion cohort (E2) will enroll up to 30 patients.

#### 2.2.2.3. MTD Definition

In Part 2, the MTD of the combinations of PF-06747143 and intensive daunorubicin/cytarabine or PF-06747143 and decitabine/azacitaditine will be determined separately within each cohort.

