#### **2.2.3. Summary**

Approximately 125-140 patients are expected to be enrolled in this study (approximately 30-50 patients in Part 1 (actual number of patients enrolled for Part 1 will depend upon tolerability of PF-06747143 and the number of dose levels required to identify the MTD) and approximately 87-102 patients in Part 2). The study will be conducted in approximately 4 sites for Part 1 and approximately 12-15 sites for Part 2.

Patients who complete the maximum number of cycles/months on study treatment (Section 3.1.2.2.1 and Section 3.1.2.2.2), demonstrate clinical benefit with manageable safety profile and are willing to continue receiving the assigned treatment may be given the opportunity to do so upon agreement between Investigator and sponsor and pending investigational product availability.

All patients who completed treatment will have a 60-day post dose follow-up period.

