#### **Primary Endpoints**

 Adverse Events as characterized by type, frequency, severity (as graded by National Cancer Institute Common Terminology Criteria for Adverse Events (NCI CTCAE) v. 4.03), timing, seriousness, and relationship to study therapy;

- Laboratory abnormalities as characterized by type, frequency, severity (as graded by NCI CTCAE v.4.03) and timing;
- Preliminary evidence of anti-leukemia activity including objective disease response; as assessed using the standardized response criteria including objective response rate (ORR), duration of ORR, and relapse free survival (RFS).(Ref 2)

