#### 4.2. Statistical Decision Rules

#### 4.2.1. Part 1

Decision rules are based on calculating unit probability mass (UPM) of three dosing intervals corresponding to under, proper, and over dosing in terms of toxicity. Specifically, the underdosing interval is defined as (0; pT-e1), the over-dosing interval (pT+e2), and the proper-dosing interval (pT-e1, pT+ e2), where e1 and e2 are small fractions. For a target DLT rate of 0.25, the target equivalence interval is (0.20, 0.30). The three dosing intervals are associated with three different dose-escalation decisions (Table 1). The under-dosing interval corresponds to a dose escalation (E), over-dosing corresponds to a dose de-escalation (D), and proper-dosing corresponds to remaining at the current dose (S). Given a dosing interval and a probability distribution, the unit probability mass (UPM) is defined as the ratio of the probability of the interval to the length of the interval. Once the safety assessment is complete for Cycle 1, the focus will be on allocation of new subjects to the dose most likely to be an MTD.

The study continues accruing until one of the three stopping conditions below is triggered. The algorithm will stop if any of the following criteria is met:

- 1. The maximum sample size has been achieved.
- 2. MTD has been identified with sufficient accuracy: at least 9 patients have been accumulated on a dose that is currently estimated to be the MTD, or
- 3. All doses explored appear to be overly toxic and the MTD cannot be determined.

Specifically the mTPI approach formalizes stopping rules as follow:

Rule 1 (early termination): if the first dose is too toxic  $\rightarrow$  Pr( $p_1 > p_T / data$ ) >  $\xi$  ;  $\xi = 0.975$ 

Rule 2 (dose exclusion), if dose= i is too toxic  $\rightarrow$  Pr( $p_i > p_T / data$ ) >  $\xi$  ;  $\xi = 0.975$  then exclude doses  $\geq i$ 

#### 4.2.2. Part 2

Part 2 of this study is intended to confirm the safety and tolerability of the dose selected in Part 1 while assessing the anti-leukemia activity of PF-06747143 in combination with standard dose of intensive chemotherapy. The DLT rate and its 95% confidence interval at the selected dose may be estimated. Part 2 data will also be used to determine the safey of combining PF-06747143 with standard chemotherapy in addition to justifying the efficacy of PF-06747143 monotherapy.

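### Part 2 expansion summaries are split by malignancy, which has one level in an AML-only study, so the planned tables do not separate Cohorts 1, 2 and 3

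*SAP*

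**What the plan says.** The design is laid out by cohort. Section 2.2 and its subsections describe Cohort 1 (fit, untreated, 7+3), Cohort 2 (unfit, untreated, with a hypomethylating drug that is "either azacitidine or decitabine, based on institutional guidelines") and an optional Cohort 3 (relapsed or refractory, single agent). Cohorts 1 and 2 each begin with a 3+3 lead-in of "approximately 3-6 patients to assure the combination treatment regimen is safe and tolerable in each patient population" (2.2.2). Section 2.2.2.3 sets the MTD cohort by cohort, treating the two hypomethylating drugs as one backbone: the MTD for "PF-06747143 and decitabine/azacitaditine will be determined separately within each cohort".

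The Part 2 primary objective (2.3.3) names the three cohorts one after another. The Part 2 primary endpoints (2.4) are AEs, laboratory abnormalities and "Preliminary evidence of anti-leukemia activity including objective disease response". Section 4.2.2 adds that "Part 2 data will also be used to determine the safey of combining PF-06747143 with standard chemotherapy" and that "The DLT rate and its 95% confidence interval at the selected dose may be estimated", without naming a regimen.

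The analysis sections use a different unit. Section 9.2.1 offers, if needed, an expansion DLT summary split by malignancy. Section 9.2.2.1 has the expansion efficacy analysis done by malignancy and tabulates response, PFS and OS overall and by malignancy. Table 2 gives malignancy as the stratum for PFS, TTP and duration of response, and dose range and malignancy for response. The AE summaries in 9.2.3 are described by grade and by cycle; no column structure is given. Covariates (7.5) are stated as not applicable.

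**The concern.** A stratifier is useful only if it has more than one level. Every cohort in this study enrols AML, so a table split by malignancy repeats the overall table. The differences that matter in Part 2 are fitness, prior treatment and partner drug. They are carried by cohort, and cohort is not named as a stratum in 9.2.1, 9.2.2.1 or Table 2.

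At stake is whether the reported Part 2 rates can be read. A response rate taken over fit patients on intensive induction, unfit patients on a hypomethylating agent and relapsed patients on the antibody alone describes no population that the objective asks about. Its value also depends on how many patients each cohort happens to enrol.

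**Working it through.** **1. The planned numbers are built by cohort.** Inputs: lead-in of about 3-6 in each of Cohorts 1 and 2 (2.2.2), up to 30 in each of E1 and E2 (2.2.2.1, 2.2.2.2), 15-30 in E3 (2.2.2.4). The stated total is "approximately 87-102 patients in Part 2" (2.2.3).

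- Lead-ins of six: 2×6 + 2×30 + 15 = 87 and 2×6 + 2×30 + 30 = 102. This matches exactly.
- Lead-ins of three: 2×3 + 2×30 + 15 = 81 and 2×3 + 2×30 + 30 = 96. This does not match.

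The total therefore counts three separate cohorts, with one lead-in of six for each combination cohort.

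**2. What each section separates.**

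| SAP section | Subject | Unit named | Separates the cohorts? |
|---|---|---|---|
| 2.2.2.3 | Part 2 MTD | cohort | yes, for the two combinations |
| 2.3.3 | primary objective | cohort | yes |
| 4.2.2 | DLT rate and CI | selected dose | not stated |
| 9.2.1 | expansion DLTs (optional) | malignancy | no |
| 9.2.2.1 | response, PFS, OS | overall and malignancy | no |
| Table 2 | response | dose range, malignancy | no |
| Table 2 | PFS, TTP, duration of response | malignancy | no |
| 9.2.3 | AEs | grade, cycle | not stated |

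**3. Weight of each cohort in a merged expansion rate.** A merged rate is Σ(nᵢ × pᵢ)/Σnᵢ, so cohort i has weight nᵢ/Σnᵢ. At full enrolment of E1 and E2:

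- E3 = 15: total 75; weights 30/75 = 40%, 40% and 15/75 = 20%.
- E3 = 30: total 90; weights 30/90 = 33% each.
- E3 not opened: total 60; weights 50% and 50%.

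The merged figure thus moves with the optional size of Cohort 3 even if no cohort's own rate changes.

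**4. What a merged rate hides (illustrative counts).** Take E1 and E2 only and 18 responders in 60, which is 30%, exact 95% CI 18.8% to 43.2%. The same line in the table arises from 9/30 and 9/30 (30% and 30%) or from 15/30 and 3/30 (50% and 10%). The planned summary cannot tell these apart.

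**5. Cost in precision of reporting by cohort.** Clopper-Pearson limits are the 2.5% quantile of Beta(x, n−x+1) and the 97.5% quantile of Beta(x+1, n−x).

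- 9/30: 14.7% to 49.4%, against 18.8% to 43.2% for 18/60.
- 5/15, the smallest planned Cohort 3: 11.8% to 61.6%.

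**6. Going one level further, to agent within Cohort 2.** The SAP gives no agent mix. Assuming 50/50, 70/30 or 80/20, the less used agent would have about 15, 9 or 6 of 30 patients. At an illustrative one-third response rate the exact intervals are 11.8% to 61.6% (5/15), 7.5% to 70.1% (3/9) and 4.3% to 77.7% (2/6), against 17.3% to 52.8% pooled (10/30).

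**The case against.** The sponsor can say that separation by cohort is evident from the whole document. The MTD is set within each cohort, and a 3+3 cannot be run without DLT counts and evaluable denominators for that cohort. The primary objective is stated by cohort, Table 2 refers to expansion cohorts in the plural, and 7.2.8 summarises ECG data by treatment and dose. The expansion DLT summary is optional, listings would let a reader trace individual DLTs, and 9.2.3 does not tell anyone to pool AEs. The study tests no hypothesis, so nothing inferential depends on the split.

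Much of this stands. Cohort-level DLT counts for the lead-ins follow from 2.2.2 and 2.2.2.3, and the silence of 9.2.3 on columns is an omission, not an instruction to merge. A sensible programmer may well produce tables by cohort.

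It does not rescue 9.2.1, 9.2.2.1 and Table 2. There the SAP names a split, and the split is empty. In Table 2, as far as the extracted layout can be read, the expansion cohorts belong with the analysis set and not with the strata. Dose range is tied by the text to Part 1 dose groups and separates no cohort. Listings give neither rates nor denominators. That 7.2.8 does name a treatment split shows that the primary-endpoint sections could have done the same.

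**Conclusion.** The point holds for the stratifier. For the expansion DLT summary and for response, PFS, TTP, duration of response and OS, malignancy has one level. Followed as written, the efficacy tables merge three populations on different regimens and do not answer the cohort-specific objective in 2.3.3. The size is modest: the study is descriptive, and no patient, dose decision or sample size is affected. The main exposure is response, a Part 2 primary endpoint. The conclusion rests on the AML-only enrolment and on the wording of the three places named; the weights in the working assume that E1 and E2 fill.

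Three stronger readings are tempting and are not supported.

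- A reader might infer that the Cohort 2 MTD is unsound because one agent could be missing from the lead-in. With six patients and assumed mixes from 50/50 to 80/20, that chance is 3% to 26%. But the SAP gives no mix, and independent choice is doubtful when the choice follows drug availability and institutional guidance. The SAP also openly declares one shared lead-in and one class-level MTD.
- A reader might infer that no denominator per cohort is planned at all. The MTD rule in 2.2.2.3 requires one.
- A reader might infer that AEs are to be pooled over regimens. Section 9.2.3 does not say so.

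**What to change.** - In 9.2.1, 9.2.2.1 and Table 2, replace malignancy with cohort (1, 2, 3) as the stratifier for Part 2. If an overall Part 2 figure is kept, label it as a mixture of regimens.
- In 4.2.2, state that the DLT rate and its exact 95% CI are given per cohort at the dose selected for that cohort.
- In 9.2.3, state that the AE summaries are presented by cohort.
- Optionally, add a descriptive azacitidine and decitabine breakdown within Cohort 2, with the pooled result kept alongside and a note that the intervals are too wide to compare the agents.

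Leave the Cohort 2 lead-in and its MTD as they are. The cost is a text edit and some table columns, with wider intervals per cohort than for a merged rate. No new data are needed: cohort is fixed at entry, and the evaluability rule in 7.2.1 already requires each combination patient's backbone dose. The change should be made before the final analysis.

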#### 2.2.2.4. Part 2/Cohort 3 – PF-06747143 Single Agent Expansion

An additional single agent PF-06747143 expansion cohort, Cohort 3 (E3), at the MTD/RP2D may be initiated in Part 2 in 15-30 refractory and/or relapsed AML patients. The initiation of this cohort will require that single agent PF-06747143 demonstrates encouraging clinical benefit (eg, significantly improved CR and response duration compared to historical data) in the dose escalation Part 1. Patients in this cohort will be treated until disease progression or relapse, patient refusal or unacceptable toxicity occurs (whichever comes first).

